3.2 Exclusion Criteria

3.2.1 Patients who have had external beam radiotherapy, cytotoxic chemotherapy, or oral multikinase inhibitors within 4 weeks prior to study enrollment.

3.2.2 Patients who have been treated with radioactive iodine within 24 weeks prior to study enrollment (radioactive iodine within 24 weeks will be allowed if negative post-treatment scan or progressive disease defined by RECIST 1.1).

3.2.3 Patients that have not recovered from adverse events related to prior chemotherapy, radiation therapy or multikinase inhibitors to CTCAE 4.0 grade 1 or less except for alopecia.

3.2.4 Patients previously treated with potent BRAF inhibitor or MEK inhibitor, including PLX4032/vemurafenib, ARQ 736 for more than 10 days. Previous treatment with sorafenib is permitted.

3.2.5 Patients that are receiving any other investigational agent.

3.2.6 Patients that are currently taking any prohibitive medication. (Appendix B). Patients on therapeutic dose of warfarin. This is due to potential for significant interactions between warfarin and study agents.

3.2.7 Patients with a known history of infection with Hepatitis B Virus (HBV) or Hepatitis C Virus (HCV).

3.2.8 Patients with a history of other malignancy. Patients who have been disease-free from other malignancy for 5 years or greater, or patients with a history of resected non-melanoma skin cancer, or patients with a history of treated in situ carcinoma will be allowed.

3.2.9 Patients with uncontrolled brain metastases. Patients who are on a stable dose of corticosteroids for more than 1 month or off corticosteroids for 2 weeks prior to study enrollment can be enrolled. Enzyme-inducing anti-epileptic drugs are not permitted.

3.2.10 Patients with a known history of retinal vein occlusion (RVO) or central serous retinopathy (CSR) or predisposing factors to RVO or CSR (e.g.

uncontrolled glaucoma or ocular hypertension, uncontrolled systemic disease such as hypertension, diabetes mellitus, or history of hyper viscosity or hypercoagulability syndromes).

3.2.11. Visible retinal pathology as assessed by ophthalmic exam that is considered a risk factor for RVO or CSR such as:

- a. Evidence of new optic disc cupping
- b. Evidence of new visual field defects
- c. Intraocular pressure > 21 mm Hg as measured by tonography

3.2.12 Patients with Class II, III, or IV heart failure as defined by the New York Heart Association (NYHA) functional classification system.

- a. Abnormal cardiac valve morphology (subjects with minimal abnormalities, can be entered on study with approval).

3.2.13 QTc interval greater than or equal to 480 msec (\geq 500 msec for subjects with Bundle Branch Block).

3.2.14 Patients with uncontrolled intercurrent illness including, but not limited to, ongoing or active infection, symptomatic congestive heart failure, unstable angina pectoris, cardiac arrhythmia, or psychiatric illness/social situations that would limit compliance with study requirements.

3.2.15 Pregnant women and nursing women are excluded from this study because Dabrafenib has the potential for teratogenic or abortifacient effects. In embryofetal developmental studies in rats, developmental toxicities including reduced fetal body weight, embryo-lethality, cardiac ventricular septal defect malformations, delayed skeletal development and variation in thymic shape have been observed.

3.2.16 HIV-positive patients or those on combination antiretroviral therapy are ineligible because of the potential for pharmacokinetic interactions with Dabrafenib. In addition, these patients are at increased risk of lethal infections when treated with marrow-suppressive therapy.

3.2.17 Subjects with a history of pneumonitis or interstitial lung disease.

3.2.18 History of acute coronary syndromes (including myocardial infarction and unstable angina), coronary angioplasty, or stenting within 6 months prior to study enrollment.

3.2.19 History of uncontrolled arrhythmias. Subjects with controlled atrial fibrillation for >1 month prior to study enrollment are not excluded.

3.3 Inclusion of Women and Minorities

Both men and women of all races and ethnic groups are eligible for this trial.

4. REGISTRATION PROCEDURES

4.1 General Guidelines

OSU patients will be registered by the OSU research coordinator.

Subsite patients will have eligibility verified and will be entered on study centrally at the Ohio State University by the Study Coordinator. All subsites should call the Subsite Coordinator, [name], at [contact] to verify slot availabilities. The required forms, including Eligibility Criteria Checklist and Registration Form, can be found in the Supplemental Forms Document.

Following registration, patients should begin protocol treatment within 5 business days. Issues that would cause treatment delays should be discussed with the Principal Investigator and Subsite Coordinator. If a patient does not receive protocol therapy following registration, the patient's registration on the study may be canceled. The Subsite Coordinator should be notified of cancellations as soon as possible.

Except in very unusual circumstances, each participating institution will order study agents directly from Novartis. Agents may be ordered by a participating site only after the initial IRB approval for the site has been forwarded to the Coordinating Center.

4.2 Registration Process

To register a subsite patient, the following documents should be completed by the research nurse or data manager and faxed or e-mailed to the Subsite Coordinator:

- Copy of all required laboratory and radiologic tests per the protocol calendar. Screening tests must be within the specified window.
- Signed patient consent form
- HIPAA authorization form
- Eligibility Criteria Checklist
- Registration Form
- Source documents verifying every inclusion & exclusion criteria
- Emails and other signed forms used as source documentation

The subsite research nurse or data manager at the participating site will then call or email the Subsite Coordinator to verify eligibility. To complete the registration process, the Coordinator will:

- assign a patient study number
- register the patient on the study
- randomize the patient to treatment ARM A or ARM B
- advise if patient will need Pharmacokinetic studies (as it is restricted to first 10 pts on each arm)
- fax or e-mail the patient study number and assigned treatment ARM to the participating site

4.3 Cross-over from Arm A to Arm B

- At the treating physician's discretion, patients that experience disease progression on ARM A, may cross over from ARM A to ARM B. Each participating center needs to re-register the patient by contacting the coordinating center with the following data: Progressive disease documentation form (e.g. local Tumor Measurement Form)
- Reports of relevant CT/MRI scans including baseline and on study until progression

Patients that cross over to ARM B will not be eligible to participate in the Pharmacokinetics (PK) or the Pharmacogenetics (PGx) correlative studies.

5. TREATMENT PLAN

5.1 Agent Administration

Patients will receive treatment depending on which treatment ARM patients are randomized to (see Figure 3. Treatment Schema). Please review entire Section 5.0 to review treatment of study agents as well as caution with concomitant medications.

[figure not shown]
Treatment will be administered on an outpatient, continuous basis. One cycle is defined as 28 days. Reported adverse events and potential risks are described in Section 7. Appropriate dose modifications are described in Section 6. No investigational or commercial agents or therapies may be administered with the intent to treat the patient's thyroid cancer.

The patient will be requested to maintain a medication diary documenting the dose of medication(s) and the date and time of each dose taken. The medication diary will be returned to clinic staff at the end of each cycle.

It is preferred that patients take all planned study agent on day 1 of each new cycle. Patients should be instructed to take scheduled doses on clinic visit days. Any dose delayed > 1 hour from scheduled time on day 1 of a new cycle due to pending safety assessments may still be taken so long as there is at least 12 hours between doses (per IBs). Alternatively, one dose of Trametinib and/or one or more doses of Dabrafenib may be missed on day 1 of a new cycle, if per local standard practice patients are

instructed by the treating physician to hold all dosing on clinic days until after the safety assessments have been completed. All missed doses and reasons are to be clearly documented in the source records and study case report forms.

Figure 3. Treatment Schema

5.1.1. Administration of Dabrafenib (BRAFi) [For ARM A and ARMB]

Dabrafenib will be taken on an outpatient basis at the dose of 150 mg orally twice a day, or approximately every twelve hours, and on a continuous basis. Dabrafenib capsules are supplied as 50 mg, and 75 mg capsules for oral administration.

Dabrafenib should be taken under fasting conditions, either one hour before a meal or 2 hours after a meal. It should be taken with approximately 240 mL (8 fluid ounces) of water at approximately the same time each day. Patients should abstain from ingestion of Seville oranges, grapefruit or grapefruit juice, pummelos, or exotic citrus fruits or grapefruit hybrids while on the study, and avoid ingestion of such fruit(s) for at least 24 hours prior to the start of dosing, due to potential increased plasma Dabrafenib concentrations due to inhibition of intestinal CYP3A4.

If a patient vomits after taking study medication, the patient should be instructed not to retake the dose and should take the next scheduled dose.

Medication should be taken within a two hour window of the scheduled dose. If a patient misses the dose (falls outside of the scheduled 2 hour window) of study medication for some reason, the patient should just skip that dose and should take the next scheduled dose.

5.1.2 Administration of Trametinib (MEKi) [For ARM B ONLY]

Trametinib will be taken on an outpatient basis at the dose of 2 mg orally once daily in the morning and on a continuous basis. Trametinib tablets are supplied as 0.5 mg, and 2 mg (as free base) tablets for oral administration.

Trametinib should be administered under fasting conditions, either one hour before or 2 hours after a meal, at approximately the same time each day. It should be taken with approximately 240 mL (8 fluid ounces) of water. If a patient vomits after taking study medication, the patient should be instructed not to retake the dose and should take the next scheduled dose.

Trametinib should be taken within a two hour window of the scheduled dose. If a patient misses the dose (falls outside of the scheduled 2 hour window) of study medication for some reason, the patient should just skip that dose and should take the next scheduled dose.

Trametinib and the morning dose of Dabrafenib may be taken at the same time.

Patients who are selected for pharmacokinetics (PK) blood draws will take Dabrafenib (BRAFi) only once in the morning (instead of twice) on C1D1 and C2D1. On these days, patients on ARM B will take their daily dose of Trametinib (MEKi) in the morning. These patients will be instructed to bring and take their study drug(s) in the clinic on C1D15 for a pre-dose PK sample. Patients will take study med(s) in the clinic on C1D1 and C2D1, as timed for PK sampling.

5.2 General Concomitant Medication and Supportive Care Guidelines

5.2.1 General Concomitant Medication Use

Because there is a potential for interaction of Dabrafenib or Trametinib with other concomitantly administered drugs through the cytochrome P450 system, the case report form must capture the concurrent use of all other drugs, over-the-counter medications, or alternative therapies.

Appendix C presents guidelines for identifying medications/substances that could potentially interact with the study agent(s).

5.2.2 Supportive Care Guidelines

Anti-emetics and anti-diarrheal treatment are not recommended for prophylactic use. Specific guidelines for management of adverse events are described in Section 6.

Proton Pump Inhibitors (PPIs) or H2 Blockers (acid reducers) may be used as supportive care for early symptoms of nausea and/or heartburn as nausea/heartburn might indicate early symptoms of gastritis/peptic ulcer that might be associated with study drugs.

5.3 Prohibited Medications

Dabrafenib induces CYP3YA-mediated metabolism, and administration of Dabrafenib with drugs that are affected by the induction of these enzymes, may result in decreased concentrations and loss of efficacy of the study drug. Drugs that are strong inhibitors or inducers of CYP3A or CYP2C8, Pgp or Bcrp transporters are contraindicated. These prohibited medications can be found in Appendix B.

5.4 Cautionary Medications

The following medications should be used with caution: (see Appendix C for a listing of these medications)

- Drugs that are substrates of CYP2C8, CYP2C9, and CYP2C19 that are highly sensitive to inhibitors or that have a low therapeutic index because concentrations of these substrates may be altered by Dabrafenib.
- Drugs that are mild/moderate inhibitors or inducers of CYP3A, CYP2C8, or Pgp or Bcrp transporter because they may alter Dabrafenib concentrations.
- Additionally, Dabrafenib may induce CYP3A4 and CYP2B6. Other enzymes such as CYP2C8, CYP2C9, and CYP2C19 may be affected as well. Co-administration of Dabrafenib and medications that are affected by the induction of these enzymes may result in loss of efficacy. If co-administration of these medications is necessary, investigators should monitor subjects for loss of efficacy or consider substitutions of these medications. The list may be modified based on emerging data.
- Patients that are taking Anti-Platelets or Anti-Coagulants such as: Aspirin, Clopidogrel, Dabigatran, Warfarin, Enoxaparin, or any other blood thinning agent, will need to have a CBC every 2 weeks during the first 4 months for close monitoring as GI haemorrhage has been seen with study drugs and above agents might increase such risk.

5.5 Duration of Therapy

In the absence of treatment delays due to adverse event(s), treatment may continue until one of the following criteria applies:

- Disease progression for patients on ARM B (Patients who develop progression on ARM A may be crossed-over to ARM B after re-registering patient with coordinating center). Disease progression in this case is defined as 20% increase in sum of index lesions compared with baseline (not the best response); or unequivocal diagnosis of new non-bony tumor lesion. Patients who are noted to have ‘new’ or ‘worsening’

bony lesions can stay on treatment if the patient has clinical benefit (it has been challenging to diagnose bony metastasis response/progression while patients are treated with such new class of drugs).

- Off of study drug continuously for more than 28 days for any reason.
- Intercurrent illness that prevents further administration of treatment,
- Unacceptable adverse event(s) or meets any dose stopping criteria (Section 6)
- Patient decides to withdraw from the study, or
- General or specific changes in the patient's condition render the patient unacceptable for further treatment in the judgment of the investigator.

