3. PATIENT SELECTION

3.1 Eligibility Criteria

3.1.1 Patients must have histologically or cytologically confirmed papillary thyroid cancer, follicular thyroid cancer (Tall cell variant, insular thyroid cancer, follicular variant of papillary thyroid cancers, poorly differentiated thyroid cancer or any of the above mixed histology will be allowed). Patients with anaplastic thyroid cancer are excluded.

3.1.2 Presence of BRAF mutation or genes fusions involving BRAF in tumor tissue.

3.1.3 Patients must have measurable disease, defined as at least one lesion that can be accurately measured in at least one dimension (longest diameter to be recorded for non-nodal lesions and short axis for nodal lesions) as ≥ 20 mm with conventional techniques or as ≥ 10 mm with spiral CT scan, MRI, or calipers by clinical exam. Malignant lymph nodes will be considered measurable if they are ≥ 15 mm in short axis. See Section 11 for the evaluation of measurable disease.

3.1.4 Patients must have progressive disease within the thirteen months prior to study enrollment. Progressive disease is as defined in RECIST 1.1, which is at least a 20% increase in the sum of diameters of target lesions and the sum must also demonstrate an absolute increase of at least 5 mm. The appearance of one or more new lesions is also considered progressive disease.

3.15 Patients must have disease that is refractory (unresponsive) to radioactive iodine (RAI) treatment as defined by one of the following:

- One or more measurable lesions that do not demonstrate RAI uptake
- One or more measurable lesions progressive by RECIST 1.1 within 12-months of prior RAI therapy and/or the appearance of one or more new lesion within 12 months of prior RAI therapy.
- Cumulative RAI dose of >600 mCi.
- Measurable disease that is Fludeoxyglucose (18F) PET scan positive.

3.1.6 Prior therapy allowed:

- 3.1.6.1 Patients may have been previously treated with up to three regimens of oral multikinase inhibitors, including sorafenib, sunitinib and pazopanib.
- 3.1.6.2 Patients may have been previously treated with external beam radiation or cytotoxic chemotherapy therapy.

3.1.7 Age ≥ 18 years.

Because no dosing or adverse event data are currently available on the use of Dabrafenib or Trametinib, each respectively as monotherapy or as combination therapy in patients <18 years of age, children are excluded from this study, but will be eligible for future pediatric trials.

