5.7 Criteria for Removal from Study

Patients will be removed from study when any of the criteria listed in Section 5.5 applies. The reason for study removal and the date the patient was removed must be documented in the Case Report Form.

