11.1.2 Disease Parameters

Measurable disease. Measurable lesions are defined as those that can be accurately measured in at least one dimension (longest diameter to be recorded) as ≥ 20 mm by chest x-ray or as ≥ 10 mm with CT scan, MRI, or calipers by clinical exam. All tumor measurements must be recorded in millimeters (or decimal fractions of centimeters).

Note: Tumor lesions that are situated in a previously irradiated area might or might not be considered measurable unless there is progression (per RECIST v1.1) in tumor lesions in the irradiated field and if radiation therapy is more than 8 weeks prior to study entry.

Malignant lymph nodes. To be considered pathologically enlarged and measurable, a lymph node must be ≥ 15 mm in short axis when assessed by CT scan (CT scan slice thickness recommended to be no greater than 5 mm). At baseline and in follow-up, only the short axis will be measured and followed.

Non-measurable disease. All other lesions (or sites of disease), including small lesions (longest diameter <10 mm or pathological lymph nodes with ≥ 10 to <15 mm short axis), are considered non-measurable disease. Bone lesions, leptomeningeal disease, ascites, pleural/pericardial effusions, lymphangitis cutis/pulmonitis, inflammatory breast disease, and abdominal masses (not followed by CT or MRI), are considered as non-measurable.

Note: Cystic lesions that meet the criteria for radiographically defined simple cysts should not be considered as malignant lesions (neither measurable nor non-measurable) since they are, by definition, simple cysts.

‘Cystic lesions’ thought to represent cystic metastases can be considered as measurable lesions, if they meet the definition of measurability described above. However, if non-cystic lesions are present in the same patient, these are preferred for selection as target lesions.

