Target lesions. All measurable lesions up to a maximum of 2 lesions per organ and 5 lesions in total, representative of all involved organs, should be identified as **target lesions** and recorded and measured at baseline. Target lesions should be selected on the basis of their size (lesions with the longest diameter), be representative of all involved organs, but in addition should be those that lend themselves to reproducible repeated measurements. It may be the case that, on occasion, the largest lesion does not lend itself to reproducible measurement in which circumstance the next largest lesion which can be measured reproducibly should be selected. A sum of the diameters (longest for non-nodal lesions, short axis for nodal lesions) for all target lesions will be calculated and reported as the baseline sum diameters. If lymph nodes are to be included in the sum, then only the short axis is added into the sum. The baseline sum diameters will be used as reference to further characterize any objective tumor regression in the measurable dimension of the disease.

Non-target lesions. All other lesions (or sites of disease) including any measurable lesions over and above the 5 target lesions should be identified as **non-target lesions** and should also be recorded at baseline. Measurements of these lesions are not required, but the presence, absence, or in rare cases unequivocal progression of each should be noted throughout follow-up.

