11.1.4 Response Criteria (Modified to define Minor Response and progressive disease category)

11.1.4.1 Evaluation of Target Lesions

Complete Response (CR): Disappearance of all target lesions. Any pathological lymph nodes (whether target or non-target) must have reduction in short axis to <10 mm.

Partial Response (PR): At least a 30% decrease in the sum of the diameters of target lesions, taking as reference the baseline sum diameters.

Minor Response (MR): 20%-29% decrease in the sum of the diameters of target lesions, taking as reference the baseline sum diameters.

Progressive Disease (PD): At least a 20% increase in the sum of the diameters of target lesions, taking as reference the smallest sum on study (this includes the baseline sum if that is the smallest on study). In addition to the relative increase of 20%, the sum must also demonstrate an absolute increase of at least 5 mm. (Note: unequivocal diagnosis of new non-bony tumor lesion is also considered progression. This is because it has been challenging to diagnose bony metastasis response/progression while patients are treated with such new class of drugs-i.e.: sometimes necrosis caused by

study drug is interpreted as ‘progression of lytic component).

Stable Disease (SD):

Neither sufficient shrinkage to qualify for MR or PR nor sufficient increase to qualify for PD, taking as reference the smallest sum diameters while on study.

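### Section 5.5 sets no new reference sum after cross-over and omits the 5 mm minimum, so read literally it can stop Arm B treatment in a crossed-over patient whose disease is stable

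*Combined protocol and SAP*

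**What the plan says.** Section 5.5 lists when treatment ends. For Arm B it is progression, and the same bullet lets Arm A patients who progress cross over after re-registration. It then defines the term: "Disease progression in this case is defined as 20% increase in sum of index lesions compared with baseline (not the best response". An unequivocal new non-bony lesion also counts. The bullet gives no minimum in millimetres. Section 5.7 makes the consequence mandatory: "Patients will be removed from study when any of the criteria listed in Section 5.5 applies".

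Two other sections define progression with an absolute minimum. Section 3.1.4 (eligibility) requires a 20% increase in "target lesions and the sum must also demonstrate an absolute increase of at least 5 mm". Section 11.1.4.1 (response assessment) measures the increase "taking as reference the smallest sum on study (this includes the baseline sum if that is the smallest on study", and adds: "In addition to the relative increase of 20%, the sum must also demonstrate an absolute increase of at least 5 mm".

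On cross-over, Section 4.3 asks the site to re-register the patient with a progression form and reports of the existing scans. There, baseline means the original Arm A scan. Section 11.1.3 limits baseline evaluations to the 4 weeks before treatment, and the closing notes of Section 10 repeat this. Neither mentions cross-over.

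**The concern.** The separate, baseline-referenced treatment rule is plainly deliberate and is not the objection. The difficulty is that one reference serves two successive treatments. A patient who qualifies for the combination because the target sum has grown 20% over baseline satisfies the rule for stopping the combination on the day it starts, unless the reference moves. Nothing in the text moves it.

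The missing 5 mm minimum raises a smaller problem. Elsewhere Section 5.5 is more lenient than Section 11. For very small target sums it becomes stricter, so an Arm B patient could be stopped, or an Arm A patient crossed over, on growth that Section 11 does not call progression.

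At stake is whether individual patients keep a drug that may be helping them, and whether the centers (four, per Section 9.1.1), reading scans locally (Section 11.1.7), apply the same rule.

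**Working it through.** **The plan's own figure.** Section 13.1.3 states 90% power at 15% versus 35% with 26 per arm and a 10-point margin. By exact enumeration, the chance that the better arm leads by at least 3/26 (the smallest count difference that reaches 0.10) is 0.8138, and the chance of an ambiguous result is 0.1805. So 0.8138 + 0.5 × 0.1805 = 0.904, which reproduces the figure. Nothing in Section 5.5 enters this calculation.

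**Notation.** B is the original baseline sum, N the smallest sum on study (N ≤ B), and x the ratio to B at cross-over. Target growth meets Section 5.5 at 1.2B and Section 11.1.4.1 at max(1.2N, N + 5 mm).

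**Cross-over (Sections 4.3 and 5.5).** At cross-over the sum is xB. If x ≥ 1.2, the stopping rule is already met. To leave the stopping range the sum must shrink by more than 1 − 1.2/x. With the reference reset to the cross-over scan, the 20% rule stops treatment at 1.2x times the original baseline.

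| x at cross-over | Shrinkage that must be exceeded | Stop after reset (× original B) |
|---|---|---|
| 1.2 | 0% | 1.44 |
| 1.3 | 7.7% | 1.56 |
| 1.4 | 14.3% | 1.68 |
| 1.5 | 20.0% | 1.80 |

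Illustrations, with B = 50 mm assumed:
- Cross at 60 mm and stay at 60 mm: 60/50 = 1.2, so the rule is met with no change on the combination. After a reset the stop is 1.2 × 60 = 72 mm.
- Cross at 65 mm and shrink to 60 mm (−7.7%): still 1.2, so still met. After a reset the stop is 1.2 × 65 = 78 mm.
- Shrink on Arm A to 30 mm, then cross at 37 mm: 37/50 = 0.74, so the target-growth criterion is not met.

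A patient who crossed for a new non-bony lesion while below 1.2B also escapes the target-growth criterion, but no text says that lesion has stopped being new.

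**The 5 mm minimum (Sections 3.1.4, 5.5 and 11.1.4.1).** With no shrinkage (N = B) the gap between the two thresholds is 5 − 0.2B. Section 5.5 comes first when N + 5 > 1.2B, that is, when shrinkage is below 5/B − 0.2.

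| B (mm) | Section 5.5 (mm) | Section 11 (mm) | Gap (mm) | Section 5.5 first if shrinkage is below |
|---|---|---|---|---|
| 10 | 12 | 15 | 3 | 30% |
| 15 | 18 | 20 | 2 | 13.3% |
| 20 | 24 | 25 | 1 | 5.0% |
| 25 | 30 | 30 | 0 | none |

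Entry requires only "at least one lesion that can be accurately measured in at least one dimension", with a 10 mm minimum for a non-nodal lesion on CT. For nodes, "a lymph node must be ≥ 15 mm in short axis when assessed by CT scan". A sum under 25 mm is therefore possible only with one non-nodal lesion of 10–24 mm, one node of 15–24 mm, or two non-nodal lesions totalling 20–24 mm. A node plus a non-nodal lesion is at least 15 + 10 = 25 mm, and any three lesions are at least 30 mm.

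After such a stop, the off-therapy column of the Section 10 calendar has no CT or MRI. The request in Section 11.1.4.3 to document progression after discontinuation is made for symptomatic deterioration.

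**The case against.** Section 11.1 says progression is evaluated in this study by RECIST 1.1, and the parenthesis in Section 5.5 flags only a change of reference sum. A site could fairly read Section 5.5 as RECIST progression measured from baseline, with the 5 mm minimum kept. On cross-over, the literal reading defeats the cross-over it permits, so investigators are unlikely to follow it. Re-registration, the 4-week limits in Section 11.1.3 and Section 10, and calendar footnotes k and n, which deal with crossed-over patients, all point towards a fresh baseline. Small target sums should be uncommon, since Section 11.1.2 makes targets of "All measurable lesions up to a maximum of 2 lesions per organ and 5 lesions in total". With 8-weekly scans in often slow-growing disease, crossing far above 1.2 times baseline may also be uncommon, and a patient who crosses at exactly 1.2 leaves the stopping range with any shrinkage.

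Much of this stands. It limits how often the rule would do harm, and many sites would probably re-baseline or apply the minimum. But it remains inference: no sentence resets the reference, and a mandatory stopping rule should not have to be set aside to be applied sensibly.

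Three stronger readings do not hold:
- A reader might infer that removal under Section 5.7 ends all observation. Section 5.6 still collects survival, disease status and later therapy every 3 months for a year, by visit or phone.
- A reader might infer that the trial's main result is compromised. Section 13.1.2 judges response before progression and excludes post-cross-over data from the decision.
- A reader might take 2 mm of growth as the typical trigger. That is the extreme case of a single 10 mm lesion.

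**Conclusion.** The point holds as a minor correction to the treatment rule. Its main part is the missing reference after cross-over. On the literal text, any patient who crossed for target growth at or above 1.2 times the original baseline meets the Arm B stop until the sum falls below that level. This assumes that baseline in Section 5.5 means the pre-Arm A scan, which the text neither confirms for crossed-over patients nor rules out. Patients who cross below 1.2 times baseline from a deep nadir are not affected by the target-growth criterion.

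The missing 5 mm minimum is secondary. It matters only for baseline sums under 25 mm with little shrinkage, and the gap is at most 3 mm. The documents do not say how many such patients there would be; probably few.

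**What to change.** 1. In Sections 5.5 and 4.3, state that after cross-over the last scan before the first combination dose is the new reference for Section 5.5, and that lesions already present on it do not count as new.
2. In Section 5.5, require a 5 mm absolute increase in addition to the 20%. The threshold becomes max(1.2B, B + 5). Since N ≤ B, this is never below max(1.2N, N + 5), so target growth under Section 5.5 can no longer come before progression under Section 11.

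Cost: wording in two sections and no extra patients. No extra scan is needed if the progression scan serves as the reference. If the 4-week limit is applied, a patient who starts the combination later than that needs one repeat scan. The case report forms are not in the documents, so a form change cannot be ruled out.

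Downsides: small-volume disease may grow up to 3 mm more before treatment stops (5 − 2 mm at a 10 mm baseline). Crossed-over patients may reach 1.44 times the original baseline or more before target growth stops them. For small sums the 5 mm minimum raises this further: a 10 mm lesion crossing at 15 mm would stop at 15 + 5 = 20 mm. The investigator-judgment stop in Section 5.5 remains in force throughout.
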